## 6.2.3. Primary Safety Endpoint

date of last tumor assessment date.

Primary safety endpoint: The overall incidence and severity of all adverse events using Common Toxicity Criteria v 4.0.

An adverse event is any untoward medical occurrence that may present during treatment with a pharmaceutical product but which does not necessarily have a causal relationship with this treatment. Adverse events (AEs) will be collected using the Leukemia AE guidelines.

Adverse drug reaction is a response to a drug which is noxious and unintended and which occurs at doses normally used in man for prophylaxis, diagnosis, or therapy of disease or for the modification of physiologic function.

All "suspected adverse reactions" (as defined in 21 CFR 312.32(a)) will be captured in the case report forms. For abnormal chemical values grade 3 or 4, the apogee will be reported per course in the CRF.

Assessing causal connections between agents and disease is fundamental to the understanding of adverse drug reactions. In general, a drug may be considered a contributory cause of an adverse event if, had the drug not been administered, 1) the event would not have happened at all, 2) the event would have occurred later than it actually did, or 3) the event would have been less severe.

The Investigator or physician designee is responsible for verifying and providing source documentation for all adverse events and assigning the attribution for each event for all subjects enrolled on the trial.

# 6.2.4. Serious Adverse Event Reporting (SAEs)

Protocol 2016-0636 Date: 06/03/2019

Page **26** of **39** 

An adverse event or suspected adverse reaction is considered "serious" if, in the view of either the investigator or the sponsor, it results in any of the following outcomes:

- Death
- A life-threatening adverse drug experience any adverse experience that places the patient, in the view of the initial reporter, at immediate risk of death from the adverse experience as it occurred. It does not include an adverse experience that, had it occurred in a more severe form, might have caused death.
- Inpatient hospitalization or prolongation of existing hospitalization
- A persistent or significant incapacity or substantial disruption of the ability to conduct normal life functions.
- A congenital anomaly/birth defect

Important medical events that may not result in death, be life-threatening, or require hospitalization may be considered a serious adverse drug experience when, based upon appropriate medical judgment, they may jeopardize the patient or subject and may require medical or surgical intervention to prevent one of the outcomes listed in this definition. Examples of such medical events include allergic bronchospasm requiring intensive treatment in an emergency room or at home, blood dyscrasias or convulsions that do not result in inpatient hospitalization, or the development of drug dependency or drug abuse (21 CFR 312.32).

 Important medical events as defined above may also be considered serious adverse events. Any important medical event can and should be reported as an SAE if deemed appropriate by the Principal Investigator or the IND Sponsor, IND office.

All events occurring during the conduct of a protocol and meeting the definition of a SAE must be reported to the IRB in accordance with the timeframes and procedures outlined in "The University of Texas M. D. Anderson Cancer Center Institutional Review Board Policy for Investigators on Reporting Unanticipated Adverse Events for Drugs and Devices". Unless stated otherwise in the protocol, all SAEs, expected or unexpected, must be reported to the IND Office, regardless of attribution (within 5 working days of knowledge of the event).

Only unexpected AEs will be recorded in the Case Report Form (CRF). The Principal Investigator will sign and date the PDMS or CORE Case Report Form toxicity pages per each patient at the completion of each course. Following signature, the Case Report Form will be used as source documentation for the adverse events for attribution.

**All life-threatening or fatal events**, that are unexpected, and related to the study drug, must have a written report submitted within **24 hours** (next working day) of knowledge of the event to the Safety Project Manager in the IND Office.

Unless otherwise noted, the electronic SAE application (eSAE) will be utilized for safety reporting to the IND Office and MDACC IRB. MDACC.

NCT ID: NCT03047993

Protocol 2016-0636 ate: 06/03/2019 Version 1

Page **27** of **39** 

Serious adverse events will be captured from the time of the first protocol-specific intervention, until 30 days after the last dose of drug unless the participant withdraws consent. Serious adverse events must be followed until clinical recovery is complete and laboratory tests have returned to baseline, progression of the event has stabilized, or there has been acceptable resolution of the event.

Additionally, any serious adverse events that occur after the 30 day time period that are related to the study treatment must be reported to the IND Office. This may include the development of a secondary malignancy.

The following SAEs are not subject to expedited reporting, but would still be included in the annual report via the SAE log.

a. Infection or cytopenias leading to hospitalization or prolongation of hospitalization Disease progression leading to death, life-threating AE, hospitalization or prolongation of hospitalization, or disability.

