## 7.6. Serious Adverse Event Reporting (SAE):

See Section 6.2.4 for detailed information regarding SAE definitions.

It is the responsibility of the PI and the research teams to ensure serious adverse events are reported according to the Code of Federal Regulations, Good Clinical Practices, the protocol guidelines, the sponsor's guidelines, and Institutional Review Board policy.

All events occurring during the conduct of a protocol and meeting the definition of a SAE must be reported to the IRB in accordance with the timeframes and procedures outlined in "The University of Texas M. D. Anderson Cancer Center Institutional Review Board Policy for Investigators on Reporting Unanticipated Adverse Events for Drugs and Devices". Unless stated otherwise in the protocol, all SAEs, expected or unexpected, must be reported to Calithera, regardless of attribution (see Section 6.2.2.3). SAE reporting will be done according to 21 CFR 312.32(c)(1)(iv) ("Sponsor must report any clinically important increase in the rate of a serious adverse reaction over that listed in the protocol or investigator brochure.").

The descriptions and grading scales found in the revised NCI Common Terminology Criteria for Adverse Events (CTCAE) version 4.03 will be utilized for adverse event reporting. (http://ctep.cancer.gov/reporting/ctc.html).

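### Section 6.2.4 keeps expected adverse events off the CRF, in conflict with Section 6.2.3 and with an all-AE primary safety endpoint

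*Combined protocol and SAP*

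**What the plan says.** Section 1.1 makes safety and tolerability primary objectives, together with clinical activity. Section 6.2.3 turns the safety part into an endpoint: "Primary safety endpoint: The overall incidence and severity of all adverse events using Common Toxicity Criteria v 4.0". Its definition of an adverse event does not require a causal link to treatment.

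On what is recorded, Section 6.2.3 makes four statements:

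- a general one: "Adverse events (AEs) will be collected using the Leukemia AE guidelines";
- a CRF rule: "All 'suspected adverse reactions' (as defined in 21 CFR 312.32(a)) will be captured in the case report forms";
- a second CRF rule, for laboratory values: "For abnormal chemical values grade 3 or 4, the apogee will be reported per course in the CRF";
- a duty on the investigator to provide "source documentation for all adverse events and assigning the attribution for each event for all subjects enrolled on the trial".

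Section 6.2.4 then gives a different CRF rule: "Only unexpected AEs will be recorded in the Case Report Form (CRF". Shortly after, it adds: "Following signature, the Case Report Form will be used as source documentation for the adverse events for attribution".

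Section 8.3 summarises safety data by frequency and percentage, by category and severity. It sets no limit by expectedness and does not say which dataset is used.

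**The concern.** Two sections give site staff different instructions about the same form, and the narrower one excludes events that the primary safety endpoint has to count. Expected events are, by their nature, the toxicities already associated with the treatment. Leaving them out would remove the known part of the safety profile and keep only the unfamiliar part. At stake is whether the trial can report its primary safety endpoint as defined, from data graded and attributed as events occur rather than rebuilt later from charts.

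**Working it through.** No sample size, error rate or event figure is involved, so the check sets the rules side by side. Adverse events are split by expectedness and by whether they are suspected reactions.

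| Kind of adverse event | CRF under 6.2.4 | CRF under the 6.2.3 suspected-reaction rule | Counts toward endpoint |
|---|---|---|---|
| Unexpected, suspected | Yes | Yes | Yes |
| Unexpected, not suspected | Yes | Not named; depends on the Leukemia AE guidelines | Yes |
| Expected, suspected | No | Yes | Yes |
| Expected, not suspected | No | Not named; depends on the Leukemia AE guidelines | Yes |

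1. **Third row: direct contradiction.** Section 6.2.3 requires the event on the CRF and 6.2.4 bars it. The word *only* in 6.2.4 leaves no way to satisfy both.

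2. **Third and fourth rows: mismatch with the endpoint.** All four rows count toward the endpoint. Under 6.2.4 two of the four are not recorded. The chemistry rule in 6.2.3 restores a peak value per course for Grade 3 or 4 abnormalities, but does nothing for lower grades, hematologic events or clinical symptoms.

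3. **If 6.2.3 prevails instead.** Suspected reactions and chemistry peaks reach the CRF. Events not suspected to be drug-related still depend on the guidelines, which are cited but not reproduced. Deleting the 6.2.4 sentence would therefore end the contradiction without, by itself, guaranteeing a dataset of all adverse events.

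4. **Attribution.** Section 6.2.3 asks for attribution of each event, while 6.2.4 names the signed CRF as the source for attribution. The attribution of an expected event kept off the CRF would have to sit in a record that 6.2.4 does not name.

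5. **Size.** Let p be the share of adverse events classed as expected. A CRF kept under 6.2.4 holds a share 1 − p of events and omits p, before any chemistry peaks are added back. The documents give no list of expected events, no value for p and no text of the guidelines, so p can only be placed between 0 (nothing lost) and 1 (everything lost). Section 2.7 describes toxicities already seen with telaglenastat, such as liver enzyme elevations and cytopenias. A value of exactly 0 would need none of these to recur, or none to be treated as expected. Nothing in the documents narrows the range further.

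**The case against.** The strongest reply accepts that the sentences conflict and disputes the consequence. The harm needs two conditions: that sites follow 6.2.4, and that the 8.3 tables come from the CRF. Neither is established. The Leukemia AE guidelines may be the working collection rule and may be broad. Several other routes also exist:

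- AE monitoring on Cycle 1 Days 1, 8, 15 and 22, on Day 1 of later cycles and at end of treatment (Sections 5.2.1, 5.2.3, 5.2.4 and 5.3);
- source documentation for all adverse events (6.2.3);
- Toxicity Summaries to the Medical Monitor after the first six evaluable patients, after the first 7, and every 7 thereafter (7.7);
- reporting of all SAEs, expected or not, to the IND Office (6.2.4);
- eCRF entry of the reason for any concomitant treatment (4.4.1).

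This stands as a limit on the consequence: expected events need not go unseen, and some could be recovered. It does not remove the defect. SAE reports cover serious events only. Concomitant-treatment entries miss untreated events and do not call for grade or attribution. The content of the Toxicity Summaries is not specified. None of these routes is named as the dataset for the endpoint.

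It may also be said that the sentence sits in the SAE section and was meant for SAEs. It says AEs. Read as SAEs, it would keep expected SAEs off the CRF and would still need correcting.

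A reader might go further and infer that DLT counting, the stopping rule or the choice of RP2D is compromised. The documents do not support that. The DLT definition in 4.1.1.2 does not exclude expected events. Sections 4.1.1 and 8.1.1 set the RP2D by DLT count, and the broader basis in 4.1.2 names no CRF source. Nor does the shortness of the first-cycle DLT window relative to total treatment measure the gap. It describes how far toxicity monitoring reaches, not how many events go unrecorded, and the hematologic DLT in 4.1.1.2 runs to six weeks in any case.

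**Conclusion.** The contradiction is certain and needs no assumption: for expected suspected reactions, 6.2.3 and 6.2.4 cannot both be obeyed. It is equally clear that a CRF limited to unexpected events cannot deliver an endpoint defined on all adverse events.

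The understatement of incidence is conditional on 6.2.4 being followed and on the 8.3 tables drawing on the CRF. Its size cannot be computed from the documents. A reader might conclude that primary safety data will certainly be lost; the text does not go that far, because 8.3 is silent on its source and 6.2.3 requires source documentation that could allow recovery.

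It should be corrected all the same, because it governs data capture for a primary endpoint and the remedy is small.

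**What to change.** - **Section 6.2.4.** Replace the sentence with a rule that adverse events are recorded in the CRF whether expected or unexpected, each with grade and attribution. Keep expectedness only as a criterion for expedited reporting.
- **Section 6.2.3.** Bring the CRF sentence and the Leukemia AE guidelines reference into line, so that what is collected supports the all-AE endpoint. The sponsor should check the guidelines first. If they exclude any events, restate the endpoint to match what is collected.
- **Section 8.3.** State that the safety tables use this dataset.

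The cost is protocol text in three places, more CRF data entry at a single institution, and possibly revised CRF toxicity pages. If any patients have already been recorded under the 6.2.4 rule, their expected events would need back-entry from source. No new patient procedures are involved.

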### Reporting to FDA:

- Serious adverse events will be forwarded to FDA by the IND Sponsor (Safety Project Manager IND Office) according to 21 CFR 312.32
- It is the responsibility of the PI and the research team to ensure serious adverse events are reported according to the Code of Federal Regulations, Good Clinical Practices, the protocol guidelines, the sponsor's guidelines, and Institutional Review Board policy.

### 6.2.5. Procedure in Case of Pregnancy

If a female subject or partner of a male subject becomes pregnant during the study dosing period or within 3 months from the discontinuation of dosing, the investigator should report the information to the study supporter as if it is an SAE. The expected date of delivery or expected date of the end of the pregnancy, last menstruation, estimated fertility date, pregnancy result and neonatal data etc., should be included in this information. The investigator will follow the medical status of the mother, as well as the fetus, as if the pregnancy is an SAE.

When the outcome of the pregnancy falls under the criteria for SAEs [spontaneous abortion, induced abortion, stillbirth, death of newborn, congenital anomaly (including anomaly in a miscarried fetus)], the investigator should respond in accordance with the report procedure for SAEs. Additional information regarding the outcome of a pregnancy (which is categorized as an SAE) is mentioned below.

- "Spontaneous abortion" includes abortion and missed abortion.
- Death of an infant within 1 month after birth should be reported as an SAE regardless of its relationship with the study drug.

NCT ID: NCT03047993

Protocol 2016-0636 ate: 06/03/2019

Page **28** of **39** 

- If an infant dies more than 1 month after the birth, it should be reported if a relationship between the death and intrauterine exposure to the study drug is judged as "possible" by the investigator.
- In the case of a delivery of a living newborn, the "normality" of the infant is evaluated at the birth.
- "Normality" of the miscarried fetus is evaluated by visual examination unless test results which indicate a congenital anomaly are obtained prior to miscarriage.

### **6.2.6. SAE Reporting to Calithera**

Any serious adverse events which occur during the clinical study or within 30 days of receiving the last dose of study medication, whether or not related to the study drug, must be reported by the investigator. In addition, any SAEs which occur as a result of protocol specific diagnostic procedures or interventions must also be reported.

All serious adverse events must be reported within 5 working days of knowledge of the event (within 24 hours for life threatening or fatal events) to Calithera Bioscience's PharmacoVigilance agent according to the Safety Data Exchange Agreement at the following:

US Toll Free [contact]

eFax forwarded to [contact]

email: [contact]

The SAE report should comprise a full written summary, detailing relevant aspects of the adverse events in question. Where applicable, information from relevant hospital case records and autopsy reports should be included. Follow-up information should be forwarded to Calithera within 24 hours.

SAEs brought to the attention of the investigator at any time after cessation of telaglenastat and considered by the investigator to be related or possibly related to telaglenastat must be reported to Calithera if and when they occur. Additionally, in order to fulfill international reporting obligations, SAEs that are related to study participation (e.g., procedures, invasive tests, change from existing therapy) or are related to a concurrent medication will be collected and recorded from the time the subject consents to participate in the study until he/she is discharged.

# 6.3. Secondary and Exploratory Endpoints:

# 6.3.1. Pharmacokinetic Analysis

NCT ID: NCT03047993

Protocol 2016-0636 ate: 06/03/2019 Version 1

Page **29** of **39** 

PK studies will be performed on plasma to assess steady-state levels of telaglenastat over time, and drug accumulation over time. PK sampling will occur on C1D15, C2D1, and C3D1.

PK assay will be conducted at a central laboratory where the assay for telaglenastat has been validated. Details are given below and in the laboratory manual:

### 6.3.2. Pharmacodynamic Analysis

Pharmacodynamic effects of telaglenastat will be measured in MDS CD34+ and in bone marrow stromal cells isolated before treatment and at all bone marrow study timepoints. These include measurements of intracellular metabolism; RNA expression of GLS and other metabolic genes; DNA methylation and hyddroxymethylation studies; quantitation of phenotypically defined MDS stem cells. These PD analyses will be performed in the laboratory of [name] and [name].

No formal statistical analysis of PDn endpoints will be performed. PDn data from each assay will be listed, and possible relationships between PK and PDn variables will be explored. Any biological activity will be described.

# 7. Regulatory and Reporting Requirements:

#### 7.1. Informed Consent:

Before a subject's participation in the clinical study, the investigator is responsible for obtaining written informed consent from the subject or legally acceptable representative after adequate explanation of the aims, methods, anticipated benefits, and potential hazards of the study and before any protocol-specific screening procedures or any investigational products are administered. A legally acceptable representative is an individual or other body authorized under applicable law to consent, on behalf of a prospective subject, to the subject's participation in the clinical study.

NCT ID: NCT03047993

Protocol 2016-0636 ate: 06/03/2019 Version 1

Page **30** of **39** 

The acquisition of informed consent should be documented in the subject's medical records, and the informed consent form should be signed and personally dated by the subject or a legally acceptable representative and by the person who conducted the informed consent discussion. The original signed informed consent form should be retained in accordance with institutional policy, and a copy of the signed consent form should be provided to the subject or legally acceptable representative.

## 7.2. Independent Ethics Committee/Institutional Review Board

A copy of the protocol, proposed informed consent form, other written subject information, and any proposed advertising material must be submitted to the IEC/IRB for written approval. A copy of the written approval of the protocol and informed consent form must be received by Calithera before recruitment of subjects into the study and shipment of investigational product.

The investigator must submit and, where necessary, obtain approval from the IEC/IRB for all subsequent protocol amendments and changes to the informed consent form. The investigator should notify the IEC/IRB of deviations from the protocol or serious adverse events occurring at the site and other adverse event reports received from Calithera, in accordance with local procedures.

The investigator will be responsible for obtaining annual IEC/IRB approval/renewal throughout the duration of the study. Copies of the investigator's reports and the IEC/IRB's continuance of approval must be sent to Calithera.

# 7.3 Subject Confidentiality

The investigator must ensure that the subject's confidentiality is maintained. On documents submitted to Calithera, subjects should be identified by their study number only. Documents that are not for submission to Calithera (eg, signed informed consent forms) should be kept in strict confidence by the investigator.

In compliance with ICH GCP Guidelines, it is required that the investigator and institution permit authorized representatives of the company, of the regulatory agency(s), and the IEC/IRB direct access to review the subject's original medical records for verification of study-related procedures and data. Direct access includes examining, analyzing, verifying, and reproducing any records and reports that are important to the evaluation of the study. The investigator is obligated to inform and obtain the consent of the subject to permit named representatives to have access to his/her study-related records without violating the confidentiality of the subject.

#### 7.4. Study Termination

Protocol 2016-0636 Date: 06/03/2019

Version 1 Page **31** of **39** 

Both Calithera and the investigator reserve the right to terminate the study according to the study contract. The investigator should notify the IEC/IRB in writing of the study's completion or early termination and send a copy of the notification to Calithera.

Subjects may be eligible for continued treatment with investigational product by extension protocol or as provided for by the local country's regulatory mechanism. However, Calithera reserves the unilateral right to determine whether to supply the investigational product, and by what mechanism, after termination of the trial and before it is available commercially.

